6.1 HIPAA Authorization

Because we have access to health data through the electronic medical record and because we are collecting some data through the electronic medical record (MoCA and use of medical services), all research team members have completed HIPAA training through the University of Iowa Hospitals and Clinics Human Resources.

7.0 Study Intervention

Intervention Description

The intervention consists of two parts, Options Counseling (OC) and Health Education (HE). The OC part includes family assessment, counseling and provision of emotional support, access assistance, and development of independent-living plans (care plans) using the Iowa's Heritage Area Agency on Aging database. The HE part includes post-diagnosis family education. Options Counselor (OC) is trained to implement these tasks through using motivational interviewing techniques. We developed seven modules of the HE toolkit based on an extensive literature review on unmet needs of families receiving diagnosis of dementia, experiences of Options Counselors, and expert reviews by experienced staff members at the local Alzheimer's Association.

Through the OC-HE intervention, we aim to minimize caregiver burden through enhancing the social support network system of the participants by providing direct access to community-based programs as well as to the Options Counselor who provides emotional support and instructions on how to form strong support networks. Lower burden and better support are associated with better patient outcomes, thus, we will also evaluate whether PWDs whose caregivers receive OC-HE intervention would use emergency or urgent medical services to a lesser extent.

Each intervention encounter will occur in a setting of the participant's choosing. Typically, the initial visit is in the home of the participant (caregiver) and involves just the participant and the Options Counselor. However, the participant is able to invite whomever they choose to come to the meeting, including the PWD. The participant may choose to have the meeting at different location if the person they are caring for lives with them and they do not want to introduce the information in this manner. Although it is preferable to have this initial visit in person, the meeting can be done via phone call or virtually through a web-conferencing if participant desires so. Normally, each home visit, or face to face meeting, lasts around 1.5 hours, however, because of the addition of the Health Education component in this particular study, we

anticipate our initial visits to take about 2 hours. After the home visit, the Options Counselor will call the participants each month for the next five months to implement follow up phone intervention sessions that will last between 30 to 60 minutes. As a rough guideline, we anticipate one to two modules to be delivered during the initial visit and one module to be delivered at each of the five follow-up phone encounters. We will provide all modules to the participants at the end of the intervention as a resource. At the end of the 6-month study intervention period, participants will have every Educational Module offered in this intervention. At the end of the study the participants will also have access to the local Area Agency on Aging to continue receiving resources, counseling and options. Through this intervention participants will not have intentional interaction with other caregivers or families that are also participating in this study.

Participants in the control group will complete baseline and 3-month and 6-month follow-up interviews. They will receive a standard information brochure from the Alzheimer's Association as part of the usual care provided at the partnering clinics. After completing the 6-month follow-up interview, these participants will have an option of receiving a phone call from an Options Counselor at their local Area Agency on Aging or receiving a contact information of their local OC if they wish to initiate the call.

8.0 Randomization

We will use a randomization scheme with a 1:1 ratio based on computer generated random numbers to assign the family to one of the two study arms. We plan to have 53 in the standard care (control) group and 53 in the intervention (experimental) group. Randomization will occur after baseline assessment. The Project Investigator and Co-Project Investigator will be responsible for handling any randomization errors.

Research Manager [name] will be responsible for maintaining the master randomization list, assigning randomization codes, notifying appropriate study staff. [name] will contact the OC-HE with the name and contact information of participants who have been assigned into the intervention arm.

We plan to maintain the assigned and blinded randomization code in an automated, computerized log that is separate from the study data

9.0 Blinding and Unblinding (Masking and Unmasking)

The student interviewer/data entry assistant will be blinded on who is chosen by random for the intervention group and will not know whose information belongs to whom.

10.0 Safety Reporting

Definition of Adverse Events

This protocol uses the definition of adverse event (AE) from the OHRP Guidance on Reviewing and Reporting Unanticipated Problems Involving Risks to Subjects or Others and Adverse Events: Any untoward or unfavorable medical occurrence in a human subject, including any abnormal sign (for example, abnormal physical exam or laboratory finding), symptom, or disease, temporally associated with the subject's participation in the research, whether or not considered related to the subject's participation in the research (modified from the definition of adverse events in the 1996 International Conference on Harmonization E-6 Guidelines for Good Clinical Practice). *See Adverse Event Form Appendix G*

Serious Adverse Events

This protocol uses the definition of serious adverse events (SAE) as defined in the OHRP Guidance on Reviewing and Reporting Unanticipated Problems Involving Risks to Subjects or Others and Adverse Events: Any adverse event that (1) results in death; (2) is life-threatening (places the subject at immediate risk of death from the event as it occurred); (3) results in inpatient hospitalization or prolongation of existing hospitalization; (4) results in a persistent or significant disability/incapacity; (5) results in a congenital anomaly/birth defects; or (6) based upon appropriate medical judgment, may jeopardize the subject's health and may require medical or surgical intervention to prevent one of the other outcomes listed in this definition. *See Serious Adverse Event Form Appendix H*

Responsibilities of NIA, IRB, DSMB, and Investigators

AEs will be reported to the University of Iowa IRB and NIA using an Adverse Event Form quarterly or as determined by the NIA. The members of the Data Safety Monitoring Board (DSMB) will receive this report prior to the scheduled board meetings.

Reporting Process

The occurrence of an adverse event (AE) or serious adverse event (SAE) may come to the attention of study personnel during interviews and intervention encounters. The PI will meet with the research team bi-weekly to conduct ongoing data and safety monitoring, and will meet bi-annually with the Data Safety Monitoring Board (DSMB) consisting of three external board members, Drs. [name], [name], and [name]. The PI will be informed of serious adverse events (SAEs) as soon as they occur and will notify the UI IRB and NIA within 24 hours of notification.

All AEs, not otherwise precluded per the protocol, will be captured on the appropriate reportable event or case report form (CRF) as provided by the University of Iowa Institutional Review Board in an online form. Information to be collected includes event description, time of onset, clinician's assessment of severity, relationship to study procedures (assessed only by those with the training and authority to make a diagnosis), and time of resolution/stabilization of the event. All AEs occurring while on study will be documented appropriately regardless of relationship to the study. All AEs will be followed to adequate resolution.

Any medical or psychiatric condition that is present at the time that the participant is screened will be considered as baseline and not reported as an AE. However, if the study participant's condition deteriorates at any time during the study, it will be recorded as an AE.

Changes in the severity of an AE will be documented to allow an assessment of the duration of the event at each level of severity to be performed. After each interview, the GAD-7 anxiety score will be calculated within two weeks of administration to identify participants experiencing elevated levels of symptoms. In addition, during each intervention encounter, the interventionist will ask the participant "Have you noticed anything different since you started the study?" Documentation of onset and duration of each episode will be maintained for AEs characterized as intermittent. *See Appendices I for OC-HE documentation and J for AEs/SAEs Listing.*

The PI or Project Manager will record events with start dates occurring any time after informed consent is obtained until 7 (for non-serious AEs) or 30 days (for SAEs) after the last day of study participation. At each study visit, the staff will inquire about the occurrence of AE/SAEs since the last visit. Events will be followed for outcome information until resolution or stabilization.

The DSMB will hold a minimum of two web-based conference calls per year (about two hours per call) to discuss protocols, progress of the intervention and research activities, and data and participant safety. The PI will prepare a Safety Report to be circulated prior to the scheduled call for DSMB members to review. The reports will contain information (i.e., AE, SAE, unanticipated problems) and analyses of study procedures, progress, and data and safety issues. Any reports to the DSMB preparing data broken down by group are only to be prepared by the statistician. The board members will review the study protocol and information presented in the report and will provide recommendations on recruitment, retention, quality control, and safety procedures while ensuring the confidentiality of the study participants and results. Through these activities, we will ensure that all protocols are conducted in compliance with the AE and SAE guidelines and reports are sent to appropriate individuals including the University of Iowa IRB and the Program Officer at the NIH.

Events of Special Interest

The interventionist, Options Counselor (OC), is trained in “Person Centered Care” through the Iowa Association of Community Providers, thus, is a mandatory reporter of any abuse to dependent adults. If the OC encounters situations that may need to be reported, the protocol established by the Heritage Area Agency on Aging will be used.

If a participant discloses potential abuse to other research staff, research staff will provide information on the Heritage Area Agency’s Elder Rights Program and a direct line phone number for them to reach a trained counselor, [contact].

Description of terms used in reporting

For adverse events (AEs) not included in the protocol defined grading system, the following guidelines will be used to describe severity.

- **Mild** – Events require minimal or no treatment and do not interfere with the participant’s daily activities.
- **Moderate** – Events result in a low level of inconvenience or concern with the therapeutic measures. Moderate events may cause some interference with functioning.
- **Severe** – Events interrupt a participant’s usual daily activity and may require systemic drug therapy or other treatment. Severe events are usually potentially life-threatening or incapacitating. Of note, the term “severe” does not necessarily equate to “serious”.

All adverse events (AEs) will have their relationship to study procedures, including the intervention, assessed by an appropriately-trained clinician based on temporal relationship and his/her clinical judgment. The degree of certainty about causality will be graded using the categories below.

- **Related** – The AE is known to occur with the study procedures, there is a reasonable possibility that the study procedures caused the AE, or there is a temporal relationship between the study procedures and the event. Reasonable possibility means that there is evidence to suggest a causal relationship between the study procedures and the AE.
- **Potentially Related** – There is some evidence to suggest a causal relationship (e.g., the event occurred within a reasonable time after administration of study procedures). However, other factors may have contributed to the event (e.g., the participant's clinical condition, other concomitant events). Although an AE may rate only as "possibly related" soon after discovery, it can be flagged as requiring more information and later be upgraded to "probably related" or "definitely related", as appropriate.
- **Not Related** – There is not a reasonable possibility that the study procedures caused the event, there is no temporal relationship between the study procedures and event onset, or an alternate etiology has been established.

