The intervention consists of two parts, Options Counseling (OC) and Health Education (HE). The OC part includes family assessment, counseling and provision of emotional support, access assistance, and development of independent-living plans (care plans) using the Iowa's Heritage Area Agency on Aging database. The Options Counselor is trained to use motivational interviewing techniques to develop family care plans, provide emotional support, and connect families to available services and programs in the community. The HE part includes post-diagnosis family education using the 7-module health education toolkit developed specifically for this study based on the literature and expert reviews. OC-HE will conduct initial assessment to determine educational needs within 2 weeks of participant's randomization into the intervention group and develop initial care plan; and will conduct 5 monthly follow-up calls to adjust the care plan and provide educational components appropriate at each point. This intervention aims to create direct links between the medical clinics, home and community-based services (HCBS), and family.

Participants assigned to the usual care control group will participate in baseline, as well as 3- and 6-months

follow-up surveys. Those in usual care group will receive a general informational brochure from the Alzheimer's Association, and will be given an option of receiving a call from their local Options Counselor after completing the 6-month survey.

Study duration is about 18 months. We aim to start participant enrollment in August, 2019, complete recruitment by September, 2020, and complete data collection by March 2021. Each participant will be enrolled in this study for about 6 months from enrollment to final interview.

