Thank you for participating in our study. We would like to ask you some questions about your experiences supporting individuals diagnosed with dementia, how you are feeling in general, about clinical or community-based services that are available, as well as some background information about you and the person who received dementia diagnosis who we refer to as “the individual” in this survey. I’m going to start with questions about your background.

Conduct Baseline Interview

After Baseline:

Thank you for taking the time to speak with me today and answer these questions. I will be sending you \$20.00 in the mail and providing a follow up call to make sure you received the money.

If participant decided not to participate:

That's ok. For our records may I ask you why you decided not to participate?

Research Assistant Script 3: 3 Month Follow-up Survey

Interviewer calls to do 3 month follow-up

Hi this is _____ at the University of Iowa College of Public Health. I am calling/here to do to do the 3 month follow-up survey for the Building a Bridge project with _____.

Before we get started, I just wanted to check and see how you are doing. Have you noticed anything different since you started the study? *If any adverse events, create an AE form and fill out.*

Thank you for participating in our study. We would like to ask you some questions about your experiences supporting individuals diagnosed with dementia, how you are feeling in general, about clinical or community-based services that are available, as well as some background information about you and the person who received dementia diagnosis who we refer to as “the individual” in this survey. I’m going to start with questions about your background.

Conduct 3 month follow-up survey

After Interview:

Thank you for taking the time to speak with me today and answer these questions. I will be sending you \$20.00 in the mail and providing a follow up call to make sure you received the money.

If participant decided not to participate:

That's ok. For our records may I ask you why you decided not to participate?

Research Assistant Script 4: 6 Month Follow-up Survey

Interviewer calls to do 6 month follow-up

Hi this is _____ at the University of Iowa College of Public Health. I am calling/here to do to do the 6 month follow-up survey for the Building a Bridge project with _____.

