Before we get started, I just wanted to check and see how you are doing. Have you noticed anything different since you started the study? *If any adverse events, create an AE form and fill out.*

Thank you for participating in our study. We would like to ask you some questions about your experiences supporting individuals diagnosed with dementia, how you are feeling in general, about clinical or community-based services that are available, as well as some background information about you and the person who received dementia diagnosis who we refer to as “the individual” in this survey. I’m going to start with questions about your background.

Conduct 6 month follow-up survey

After Interview:

Thank you for taking the time to speak with me today and answer these questions. I will be sending you \$20.00 in the mail and providing a follow up call to make sure you received the money.

Thank you for participating in this study. Your participation is now complete. You can contact me at _____ if you have any further questions. You will receive your \$20 reimbursement and a letter that will let you know how you can find the results of this study and who to contact with further questions.

If participant decided not to participate:

That's ok. For our records may I ask you why you decided not to participate?

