Interventions are ongoing and flexible to meet the needs of the individual family. Following the standard OC protocol, the family receives an initial telephone intervention (previously in-person home visit, but occurred over the phone due to the pandemic) by the interventionist. During the initial call, the OC uses assessment tool to identify caregiver/family needs and develop family action plans to connect families directly to services and programs available in the area. The interventionist also conducts an assessment to determine educational needs, then conducts 2 additional monthly follow-up calls to adjust the care plans and to provide educational components appropriate at each point (3-month intervention). This program, thus, creates direct links between the medical clinics, HCBS, and family. The OC tailors the information provision to meet the needs of those receiving it by providing additional information as the time progresses, allowing the recipients to identify their concerns at the moment and presenting materials to address expressed concerns. Participants receive all educational materials and a brief overview of contents at the end of the 3-months intervention period, including the topics that may not have been covered in great detail during the intervention calls. The Area Agency on Aging provides continued support to individuals who need their services after the completion of the intervention.

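### Adverse events are asked about up to 8 times in the intervention arm (5 under the SAP schedule) and twice in controls, so any by-group summary is biased toward an apparent intervention excess

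*Protocol*

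**What the plan says.** Protocol section 10.0 states that "during each intervention encounter, the interventionist will ask the participant" a scripted open question. Appendix V puts the same question, "Have you noticed anything different since you started the study", at the start of the 3-month and 6-month survey scripts, which both arms receive. The baseline script has no such question.

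Intervention contacts:
- Protocol section 2.0: "OC-HE will conduct initial assessment to determine educational needs within 2 weeks of participant's randomization into the intervention group".
- Protocol section 7.0: "the Options Counselor will call the participants each month for the next five months to implement follow up phone intervention sessions".
- The SAP's overview of the intervention describes a shorter programme. After the initial call the interventionist "then conducts 2 additional monthly follow-up calls to adjust the care plans".

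Control contacts: section 7.0 says that "Participants in the control group will complete baseline and 3-month and 6-month follow-up interviews", and lists nothing else before the 6-month interview is done.

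Reporting: section 10.0 says "Any reports to the DSMB preparing data broken down by group are only to be prepared by the statistician". Section 15.0 lists AE and SAE incidence among the contents of the monitoring report without saying that it is split by arm. The SAP has no safety analysis. Neither the AE form (Appendix G) nor the AE/SAE listing (Appendix J) has a field for how an event came to light. Neither document mentions the unequal questioning.

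**The concern.** Asking more often, over shorter intervals, finds more events. Three features make this trial sensitive to that. The question is open-ended. The AE definition in section 10.0 takes in any symptom. A worsening of a condition present at screening also counts. Mild and short-lived events are the ones most easily forgotten between surveys.

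The extra contacts could also affect causality grading. Section 10.0 lets an AE be graded as related on a temporal relationship to study procedures, and each intervention call is a study procedure.

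A DSMB given counts by arm, with no source of detection, could take an artefact of questioning for harm. It could equally dismiss a real signal as artefact. The efficacy outcomes are not affected.

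**Working it through.** The documents give no AE rate, recall assumption or count of enquiries, so there is no stated figure to reproduce.

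**1. Scripted enquiries per participant**
- Intervention, Protocol schedule: 1 initial + 5 monthly + 2 surveys = 8.
- Intervention, SAP schedule: 1 initial + 2 monthly + 2 surveys = 5.
- Control: 2 surveys = 2.

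Section 10.0 also has staff ask about AEs at each study visit. If that includes baseline, each count rises by one (9 or 6 against 3) and the gap is unchanged.

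**2. Simple next-enquiry calculation**

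Assume equal true risk, events spread evenly in time, one chance of report at the next enquiry, and recall that halves every h months. The mean share captured when asking every T months is (1 − 2^(−T/h)) / (T·ln2/h). The Protocol ratio is the monthly share over the 3-monthly share. For the SAP schedule, monthly asking covers only the first half, so the ratio is ((monthly + 3-monthly)/2) / 3-monthly.

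| h (months) | Monthly | 3-monthly | Protocol ratio | SAP ratio |
|---|---|---|---|---|
| 1 | 0.72 | 0.42 | 1.71 | 1.36 |
| 2 | 0.85 | 0.62 | 1.36 | 1.18 |
| 3 | 0.89 | 0.72 | 1.24 | 1.12 |

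**3. Fuller model**

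The scripted question looks back to study start, so an event can be reported at any later enquiry. Put surveys at months 3 and 6, and intervention contacts at 0.5, 1.5, ..., 5.5 (Protocol) or 0.5, 1.5, 2.5 (SAP); these contact times are assumed. The chance of recording is 1 − Π(1 − p·0.5^(lag/h)) over later enquiries, where p is the chance of reporting a fresh event when asked. Ratios use unrounded shares.

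| h (months) | p | Control | Protocol | SAP | Protocol ratio | SAP ratio |
|---|---|---|---|---|---|---|
| no decay | 1.0 | 1.000 | 1.000 | 1.000 | 1.00 | 1.00 |
| no decay | 0.8 | 0.880 | 0.975 | 0.895 | 1.11 | 1.02 |
| no decay | 0.5 | 0.625 | 0.884 | 0.695 | 1.41 | 1.11 |
| 3 | 1.0 | 0.766 | 0.988 | 0.854 | 1.29 | 1.11 |
| 3 | 0.5 | 0.417 | 0.797 | 0.555 | 1.91 | 1.33 |
| 1 | 1.0 | 0.432 | 0.894 | 0.646 | 2.07 | 1.49 |
| 1 | 0.5 | 0.220 | 0.589 | 0.375 | 2.68 | 1.71 |
| 0.5 | 0.5 | 0.119 | 0.390 | 0.243 | 3.28 | 2.04 |

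The second chance at month 6 adds little for controls (0.42 to 0.43 at h = 1, p = 1). The repeated chances add much more in the intervention arm (0.72 to 0.89 under the Protocol schedule).

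**4. Chance of a nominally significant false excess**

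Take 53 per arm, two-sided 0.05, and the share with at least one recorded AE as 1 − exp(−λ × captured share), with λ = 0.3 or 0.6 AEs per person over six months (assumed). For example, with h = 3, p = 1, λ = 0.6 and the Protocol schedule, 0.447 against 0.369 gives 13%. Over p from 0.5 to 1 and both values of λ:
- Protocol schedule: 9 to 43% at h = 3 and 33 to 60% at h = 1.
- SAP schedule: 4 to 11% at h = 3 and 12 to 20% at h = 1.

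Without the bias the figure is 2.5%. The 25% attrition that Protocol section 5.0 allows for would lower these chances.

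**5. After the fix**

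On the two common surveys, enquiries are 2 against 2.

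**The case against.** The strongest reply is that no by-arm AE comparison is planned. The sentence in section 10.0 on group-level reports restricts who may prepare them; it does not call for an AE table by arm. Section 15.0 lists AE incidence without a split, and the SAP has no safety comparison. This stands: a reader might infer that unequal counts will be put before the DSMB, but the documents only make that possible.

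A reader might also infer that such a table is certain to show an excess. The documents do not support that either. The scripted question covers the whole study period at both surveys, so controls can report early events late, and with complete reporting and no forgetting the ratio is exactly 1.0. Deaths and hospitalizations should be much less affected than minor symptoms.

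Some safeguards are already even-handed. The survey question is identical in both arms, the GAD-7 is scored after every interview in both, and a trained clinician grades relatedness. The DSMB reviews the protocol, in an advisory role for a minimal-risk trial. These limit the consequences but do not equalise the number of enquiries.

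The 8-to-2 count belongs to the Protocol schedule. The SAP of January 2022 describes the shorter programme, for which 5 to 2 applies and the bias is smaller. The documents do not say how many participants followed each schedule.

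Finally, a survey-only comparison could reverse the bias. If events already told to the interventionist were left out when repeated at a survey, the intervention arm would lose events that controls keep. That is a fair warning, and the fix has to meet it.

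**Conclusion.** Questioning about AEs is structurally unequal, 8 to 2 or 5 to 2, and neither document deals with it. Any by-group AE summary is therefore biased toward an apparent excess in the intervention arm, chiefly for mild and transient events. The direction is clear once reporting is imperfect or recall fades; the size is not known.

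For recall half-lives of 1 to 3 months, the simple calculation gives ratios of about 1.2 to 1.7 (Protocol schedule) and 1.1 to 1.4 (SAP schedule). The fuller model gives 1.29 to 2.68 and 1.11 to 1.71. These rest on assumed recall, reporting probabilities and contact times, and on equal true risk. The conclusion is conditional on a by-group summary being made, which the Protocol permits but does not require. It is a reporting weakness worth correcting because correction is cheap.

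**What to change.** - Add a source-of-detection field (3-month survey, 6-month survey, intervention contact, other) to the AE form in Appendix G and the listing in Appendix J. Allow more than one source per event.
- In any by-group DSMB or final report, show all AEs by arm and source.
- Base the between-arm comparison of non-serious AEs on events reported at the 3- and 6-month surveys, using the scripted question with its look-back to study start in both arms. Section 10.0 elsewhere describes a look-back to the last visit, so state which applies.
- Count every event reported at a survey, even if the interventionist already knew of it.
- Put events found only at intervention contacts in a separate row.
- Report all SAEs in full, whatever the source.

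The cost is one form field and a table layout with a footnote. The downside is fewer events in the comparative table. Some participants may not repeat what they have already told the interventionist, which would bias the comparison the other way; the footnote should say so. The Protocol planned to finish data collection by March 2021. If it has closed, source would have to be assigned from the interview and intervention records where they allow it, with the remainder shown as unknown.
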